pregnant women. Treatment is commonly associated with headaches. Meta-analysis has suggested that treatment of hypertension with nifedipine may increase the risk of preeclampsia (OR 1.4 [1.06, 1.86])¹⁵ Treatment may be associated with a widened pulse pressure suggesting, with the incidence of headaches, that it may not be neuro-protective.¹⁶

Study Purpose

This trial will compare the efficacy, safety and side effects of these three oral regimens for management of severe hypertension in pregnant women. We hypothesize that nifedipine treatment of severe hypertensive parturient women is more effective than treatment with labetalol or methyldopa in controlling high blood pressure within six hours.

OBJECTIVES

Primary aim: To compare the efficacy of oral labetalol, oral nifedipine, and oral methyldopa for management of severe hypertension in pregnant women.

Secondary aims:

- To assess adverse outcomes and necessity for additional hypertensive treatment among women in the three study arms.
- To assess maternal and fetal outcomes among women in the three study arms

STUDY METHODS

Design

This is a pragmatic, open-label, randomised control trial of three oral anti-hypertensive regimens for women with severe hypertension in pregnancy. Women presenting with severe hypertension in pregnancy in two hospitals in Nagpur, India

will be randomised to one of three oral regimens: nifedipine, labetalol or methyldopa.

Study population

Pregnant women ≥ 18 years old and ≥ 28 weeks' gestation who have been determined to require pharmacological blood pressure control for severe hypertension defined as blood pressure $\geq 160/110$ mm of Hg, measured twice, 15 minutes apart with the woman sitting quietly for several minutes, the arm cuff at heart level, and diastolic pressure designated at the 5th Korotkoff sound, will be eligible for the trial. The relatively high entry criteria are chosen to avoid enrolling patients who might sufficiently improve without pharmacological treatment.

Two public hospitals in Nagpur, India – Government Medical College, Nagpur and Daga Women's Hospital, Nagpur – will be involved in this study. Together both hospitals have approximately 2,000 deliveries per month. Both hospitals have experience in the conduct of clinical trials, especially among this patient population. They encounter all the difficulties associated with low resource settings, but are also the site of an efficient and well run university department.

Number of Participants

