After receiving written consent from the participant, the next consecutive, sequentially numbered opaque envelope will be withdrawn from the study dispenser. A card indicating the woman's treatment assignment will be included in the envelope. The card designating the treatment group will be attached to Form 1. The group assignments will be randomised independently using a computerised pseudo-random number generator; the randomisation will be stratified by centre.

Treatment Allocation

Sequence generation will be through a random sequence allocation computer programme. The provider will not be blinded to the treatment allocation.

The clinicians in both centres will undergo training in the use of the three treatment regimens. Guidelines for the management of treatment will be drawn up in collaboration with those in the centres so as to prevent operator bias through protocol deviations. The outcome data will be collected prospectively by study staff in order to ensure that the data collection is as complete as possible. Identical data tables will be used for the data monitoring committee and the final report in order to prevent reporting bias.

Study Interventions

Women in **Group A** will receive an initial dose of oral nifedipine 10mg. If blood pressure exceeds 155mmHg systolic OR 105 mmHg diastolic after 1h, an additional 10mg dose can be provided each hour for two additional doses (30 mg total).

Women in **Group B** will receive an initial dose of oral labetalol 200mg. If blood pressure exceeds 155mmHg systolic OR 105 mmHg diastolic after 1h, an additional 200mg dose can be provided each hour for two additional doses (600 mg total).

Women in **Group C** will receive an initial dose of oral methyldopa 1000mg. No additional escalation in dose in the first 6 hours will be given.

A range is provided in the threshold for dose escalation to permit input from clinical judgment. The maximum doses are based on the upper limits of effective dose range for each medication over 24 hours: nifedipine – 120mg; labetalol 2400mg; methyldopa – 2000 mg. The treatment goal (defined as 120-150 mmHg systolic and 70-100 mmHg diastolic) has been chosen based on NICE criteria. The relatively wide range between entry criteria and treatment goal should offer the best opportunity to discover differences in clinical response.

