Successful outcome will be considered blood pressure that reaches the target (defined as 120-150mmHg systolic and 70-100 mmHg mm Hg diastolic) within 6h without an adverse outcome. Adverse outcomes include hypotension (systolic blood pressure, <120 mm Hg and/or diastolic blood pressure <70 mm Hg and fetal compromise), caesarean section for fetal distress within or up to 2 hours after the end of the study period, severe headache and severe headache requiring discontinuation of drug, or eclampsia.

Additional maternal outcomes:

- the number of BP measures above target range
- the number of BP measures below target range
- placental abruption
- maternal side effects associated with deteriorating maternal preeclampsia or the need to change drug regimen,
 - chest pain
 - dyspnea
 - headache
 - visual symptoms (flashes, diplopia)
 - epigastric or right upper quadrant abdominal pain

- nausea or vomiting.
- maternal mortality
- maternal morbidity during or up to two hours after the study period
 - eclampsia or seizure,
 - adverse CNS outcome (stroke, cortical blindness)
 - HELLP syndrome
 - pulmonary edema (O₂ sat < 90%, abnormal chest x-ray)
 - oliguria (<25 cc/hr for 2 hours)
 - disseminated intravascular coagulation
- Caesarean delivery
- Enrollment to delivery interval

Perinatal outcomes:

- stillbirth
- neonatal death
- admission to neonatal special care unit
- neonatal morbidity
 - Apgar < 7 at 5 minutes
 - intubation at place of delivery
 - mechanical ventilation beyond resuscitation
 - respiratory distress syndrome (RDS) requiring O₂ supplementation
 - abnormal cerebral ultrasound
 - convulsions
 - bradycardia (sustained HR < 100) beyond resuscitation and requiring intervention

Measures of the use of maternal health-care resources:

- number of days in the hospital
- admission to an intensive care unit or a high dependency unit
- mechanical ventilation (any)
- dialysis

- blood transfusion

Measures of the use of neonatal health-service resources:

- days in special care baby unit
- days of oxygen use
- days of mechanical ventilation

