Form 2: Monitoring Form (0-6h): This form will record the actual (rather than protocol) time for the administration of each dose. Assessment of blood pressure and pulse will be recorded every 20 minutes. Oxygen saturation will be measured and recorded every 2h. Maternal side effects including headache pain, nausea and vomiting, visual disturbances, urine output, right upper quadrant and epigastric pain will be assessed and recorded at the start of antihypertensive treatment (0h), 2h, 4h, and 6h. The Glasgow Coma Scale will be administered at 0, 2, and 6h by the attending research clinician. Although not specifically designed for this use, it is the best tool for assessment in this clinical environment. The utility of this tool for this trial will be assessed during the pilot study.

Form 3: Laboratory Results: This form will record the results of all laboratory tests. Liver enzyme tests, creatinine and platelet counts will be performed at 0h and 6 hours.

Form 4: Maternal Outcomes: The clinician will also note the final outcome of the woman including any interventions undertaken during labor and delivery. This information may be abstracted from patient charts if available.

Form 5: Neonatal Outcomes: The clinician will also note the final outcome of the baby including any interventions undertaken during labor and delivery. This information may be abstracted from patient charts if available.

Form 6: Exit Interview: The interview with the woman will be conducted once she is stable and prior to her discharge from the study hospital. This form will record her attitudes and opinions regarding the mode of treatment including experience with pain and side effects.

Form 7: Case Summary. Clinicians will complete a case summary form for each woman after she is discharged from the study. The form will summarize data recorded on other forms and confirm the number of doses administered, adverse events, and treatment discontinuation.

STATISTICS AND DATA ANALYSIS

Sample Size Calculation

The primary outcome will be control of high blood pressure (defined as 120-150mmHg systolic and 70-100 mm Hg diastolic) within 6h.

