The study results will be published in an international medical journal at the end of the study, and presented at international professional and medical research meetings. The final publication will be open access. Study results will also be disseminated on the Gynuity websites and in in-house publications, including Gynuity's research briefs, both of which are designed to make scientific results accessible to a lay audience. In India, study findings will be presented at the annual meetings of the state and national conferences of the Federation of Obstetricians and Gynaecologists of India (FOGSI).

Intellectual Property/Commercial Exploitation

This research does not use any technology or other invention that is participant to patents or other forms of intellectual property protection. The proposed research will be conducted by a collaboration of three organizations and contracts will be drawn up between all relevant parties. The data could be used to register a new indication for the drugs involved in the trial, but the study team deems this unlikely given that all three drugs are already widely currently used. The study does not require the collection of any tissues or samples from human participants.

PHARMACOVIGILANCE

Risks to the Participants

Treatment with any antihypertensive medication is associated with the risk of hypotension or low blood pressure. These risks are extensions of the beneficial effects of the medications – treatment of hypertension, high blood pressure. Symptoms associated with low blood pressure may include dizziness, light headedness and fatigue. Low blood pressure can potentially adversely affect the fetus due to poor utero-placental perfusion associated with hypotension. These are, in general, dose dependent complications. Patient will be treated in a hospital

environment with close monitoring of blood pressure. To address the possibility of excessive under-treatment, aggressive oral regimens have been designed. The clinical team will remain "in charge" and have the autonomy to address issues of clinical under-treatment or concerns regarding impending over treatment.

The drug of choice for management of severe hypertension in pregnancy at the study sites is oral nifedipine 10mg-20mg. Headache is a common complication of treatment of blood pressure with medications that are pure vasodilators. Treatment with nifedipine is associated with the development of headaches (12-16%).^{18,19}

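### Unblinded, undefined severe headache can turn a woman at target into a failure, and no listed percentage shows target attainment within 6h regardless of adverse outcome

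*Protocol*

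**What the plan says.** Design and assessment. The Design section states: "This is a pragmatic, open-label, randomised control trial of three oral anti-hypertensive regimens for women with severe hypertension in pregnancy". Treatment Allocation adds that "The provider will not be blinded to the treatment allocation" and that "The outcome data will be collected prospectively by study staff in order to ensure that the data collection is as complete as possible". No blinded assessor or adjudication is described.

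Outcome. Study Outcomes defines success as reaching 120-150 mmHg systolic and 70-100 mmHg diastolic "within 6h without an adverse outcome. Adverse outcomes include hypotension", and the list of adverse outcomes ends with "severe headache and severe headache requiring discontinuation of drug, or eclampsia". No severity scale or onset time is attached to the headache item. Side effects, including headache, are recorded from 0h on Form 2.

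Primary outcome. Three sections describe it differently:

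- Sample Size Calculation: "The primary outcome will be control of high blood pressure (defined as 120-150mmHg systolic and 70-100 mm Hg diastolic) within 6h". There is no adverse-outcome clause.
- Study Outcomes: target within 6h and no adverse outcome.
- Data Monitoring Committee: target at 6h and no adverse outcome. The interim stopping rule is tied to this version.

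Expectation about headache. Under Risks to the Participants the protocol says: "Treatment with nifedipine is associated with the development of headaches (12-16" (a percentage range, for headache of any severity). The same section names nifedipine as the study sites' drug of choice.

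**The concern.** Cuff-measured blood pressure is objective. Grading a headache as severe is a judgement, made here by staff who know the treatment and have been told that one drug commonly causes headache. Because the grade can reclassify a woman from success to failure, differential grading would enter the primary comparison directly.

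The 75% and 62.5% behind the sample size are described as control of blood pressure. If the analysis uses only the composite, no result on the woman-level scale shows whether an arm lost on pressure or on headache. Treatment Allocation also commits to identical tables for the monitoring committee and the final report, so the same gap would carry into the interim review.

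Separately, a headache that was already severe before the first dose counts as a failure as the text stands. Randomisation makes this even between arms on average, so it is not bias. It does add failures that treatment did not cause.

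**Working it through.** **1. The plan's own figure.** Inputs from Sample Size Calculation: p1 = 0.75, p2 = 0.625, two-sided alpha 0.05 with Bonferroni over two comparisons (0.025 each), power 80%. With p̄ = 0.6875:

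n = [z(0.9875)·√(2p̄(1−p̄)) + z(0.80)·√(p1(1−p1)+p2(1−p2))]² / (p1−p2)²

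= [2.2414 × 0.6555 + 0.8416 × 0.6495]² / 0.125² = 260.1, rounded up to **261**. This matches the protocol. Power at 261 per arm is 80.2%.

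**2. Which listed analyses show blood pressure alone?** From Proposed Analyses and Study Outcomes:

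| Listed item | Free of the adverse-outcome condition? | Proportion of women reaching target? |
|---|---|---|
| % at target within 6h | no | yes |
| % at target within 3h | no | yes |
| % at intermediate target within 6h | no | yes |
| % of time in target range | yes | no |
| Numbers of readings above and below range | yes | no |
| % with an adverse outcome | not applicable | no; pools hypotension, caesarean, headache and eclampsia |
| Regression on attainment of the treatment goal | unclear | yes |

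The treatment goal is defined elsewhere by pressure limits only, so the regression may model control alone or the composite. The text does not say which. Nothing else in the list gives the proportion reaching target within 6h whatever the adverse outcomes. Subtracting the pooled adverse-outcome percentage does not recover it, because that percentage includes women who never reached target.

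**3. Size, as an illustration.** The protocol gives any-headache rates of 12-16% and no severe share. Assume that 25% to 33% of these are graded severe, among the 75% of nifedipine women at target:

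- low: 0.75 × 0.12 × 0.25 = 0.0225
- high: 0.75 × 0.16 × 0.33 = 0.040

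That is about 2 to 4 points. Power = Φ{[(p1−p2)√n − 2.2414·√(2p̄(1−p̄))] / √(p1(1−p1)+p2(1−p2))} with n = 261:

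| Assumed loss | Nifedipine | Comparator | Power |
|---|---|---|---|
| none | 75% | 62.5% | 80% |
| nifedipine 2 points | 73% | 62.5% | 63% |
| nifedipine 4 points | 71% | 62.5% | 43% |
| nifedipine 4, comparator 2 | 71% | 60.5% | 61% |
| 2 points in both | 73% | 60.5% | 79% |

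For the third row: (0.085 × 16.155 − 2.2414 × 0.6662)/0.6635 = −0.181, and Φ(−0.181) = 0.428.

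**4. Headache already present at 0h.** If an assumed 5% of at-target women in both arms fail for it, the rates become 71.25% and 59.375% and power is 73%. At 10% they become 67.5% and 56.25%, and power is 66%. This is dilution, not bias.

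**The case against.** Several counter-arguments have force.

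- A reader might infer that blood pressure is never analysed alone, so that detection bias cannot be told apart from drug effect. The protocol does not support that. Time in range and counts of readings out of range are planned without any adverse-outcome condition, readings are taken every 20 minutes by automatic cuff, and adverse outcomes are reported by regimen. This stands, and it limits the point to the woman-level proportion.
- A reader might also infer a demonstrated bias against nifedipine. That is not shown either. Headache is expected with nifedipine, but it is also the sites' usual drug and the hypothesised winner, so expectation could work the other way.
- The power figures are soft. The severe share is assumed. Headache is also listed among symptoms of deteriorating preeclampsia, so the comparators will have some. The 75% was reached from a published 83% that already excluded adverse outcomes, so it may be partly net of headache. A genuine drug-induced severe headache is meant to count as failure, so lost power is not all bias.
- Supportive tables for a composite are often left to a statistical analysis plan, which is not at hand. This is fair for component tables taken alone. It does not cover a protocol that names control alone as primary in one section and the composite in another, and then lists no proportion matching the former.

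**Conclusion.** The point holds in limited form. In an open-label trial, an undefined severe headache of any onset can reverse a woman's success, and no listed percentage isolates target attainment within 6h from that reversal. The objective summaries that are planned measure something else: they cannot show how many women the headache item moved from success to failure.

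The effect could be material. Power falls from 80% to between 63% and 43% if only nifedipine loses 2 to 4 points. It is 61% when the losses are 4 and 2, and 79% when both arms lose 2. These figures assume that 25-33% of headaches are severe, that 75% and 62.5% are control rates before any headache failures, and that 261 women per arm are evaluable. They show sensitivity. They do not estimate bias, and they do not establish its presence or direction.

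The change is worth making because it is cheap and puts a result on the scale of the trial's own hypothesis.

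**What to change.** 1. Reconcile the primary outcome across Study Outcomes, Sample Size Calculation and Data Monitoring Committee: control alone or composite, and within 6h or at 6h. State which one the regression on treatment-goal attainment uses.
2. Prespecify, beside the composite, the proportion of women reaching target within 6h by automatic-cuff readings regardless of adverse outcome, and report each adverse-outcome component by arm.
3. For the outcome definition only, state how severe headache is graded and count it as a failure only when it is new or worse than the 0h assessment. This leaves clinical management untouched.

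The cost is one extra table and a short definition. The readings and the 0h assessment are already on Form 2, so no new data, staff or blinding are needed. Grading stays unblinded, but its influence on the primary result becomes visible.

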If the treatment goal (defined as 120-150 mmHg systolic and 70-100 mmHg diastolic) is achieved at 6h, treatment will be continued up to 24 hours postpartum unless deemed clinically unnecessary after delivery. The ongoing dose will be determined by the clinical care team based initially on the dose required over the first 6 hours and the clinical response after 6 hours. If the treatment goal is not achieved at 6h, women will receive the standard of care treatment for this indication. Women in the nifedipine group who do not achieve the treatment goal will continue to receive nifedipine 10mg. Women in the labetalol group who do not achieve the treatment goal will receive labetalol 200mg and women in the methyldopa group will receive either nifedipine 10mg or labetalol 200mg according to the treating physician's preference. In all cases, blood pressure monitoring will occur regularly as per standard hospital practice. During the treatment of a patient, the clinical team can determine that the study protocol should be discontinued due to 1) ineffective response resulting in clinically unsafe blood pressures or 2) significant side effects. Indications for stopping the treatment protocol will be recorded and study endpoints will be collected. Prior to and after enrollment in the trial, women in all groups should be treated with magnesium sulfate if clinically indicated and as per the standard treatment protocols at each facility. The use of magnesium sulfate and nifedipine together does not increase

the risk of serious magnesium-related side effects including hypotension (Magee et al 2005).

After the administration of the drugs, blood pressure and pulse will be recorded every 20 minutes. Blood pressure will be measured with an automatic digital blood pressure cuff. Oxygen saturation will be measured and recorded every 2h until 6h. The Glasgow Coma Scale will be administered by a research clinician at 0, 2, and 6h. AST (liver enzyme test), platelet count and creatinine will be performed at the start of antihypertensive treatment (0h), and 6 hours. Maternal side effects will be assessed at 0h, 2h, and 6h. Fetal heart rate will be recorded at 0 and 6h.

Study Outcomes

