Logistic, Poisson and negative binomial regression models will be used as appropriate to estimate effect size (difference in attainment of treatment goal rates) with 95% confidence intervals. Adjustments in 95% confidence intervals will be made for important confounding variables and covariates including: mean arterial pressure at the initiation of therapy; heart rate at the initiation of therapy; mode of admission; evidence of abnormal laboratory results; history of chronic hypertension; diabetes (gestational or medicated); gestational age; and birth weight percentile. The primary analysis will be done according to intention to treat. If indicated, a secondary, per protocol analyses will be performed. Similar regression models will be used to compare the two study groups with respect to other important (secondary) variables.

TRIAL MANAGEMENT AND OVERSIGHT ARRANGEMENTS

Trial Sponsorship

University of British Columbia

Trial Management

The study team at Gynuity Health Projects and GMC Nagpur will develop the study materials in line with the protocol. The day-to-day running of the study will be the responsibility of the Gynuity-Nagpur team who have extensive experience in conducting high quality studies in low resource settings. Prior to the start of the trial, the required local and national ethical approvals will be obtained by the Gynuity-Nagpur team who will also develop the trial documentation including data collection forms, patient information leaflet, consent form and trial standard

operating procedures (SOPs). Randomisation will be by means of random numbers centrally generated in distinct blocks. Randomisation and packaging will be by Gynuity Health Projects by staff not otherwise involved in the study. Gynuity-Nagpur will also train the local research team, manage routine trial logistics, establish a standard data entry system for trial data, supervise data entry, conduct quality checks on data entry system, and establish a backup system for trial database and relevant electronic files.

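### The primary outcome has no rule for a woman brought into range before 6h by a drug other than the one allocated, so she can count as a success of the drug that failed her

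*Protocol*

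**What the plan says.** Protocol, Study Outcomes: "Successful outcome will be considered blood pressure that reaches the target" "within 6h without an adverse outcome". The events that cancel success are hypotension with fetal compromise, caesarean section for fetal distress, and "severe headache and severe headache requiring discontinuation of drug, or eclampsia". Discontinuation appears in that list only in connection with headache.

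Protocol, Study Interventions: "the clinical team can determine that the study protocol should be discontinued due to 1) ineffective response resulting in clinically unsafe blood pressures", or because of significant side effects. No earliest time is set. Then: "Indications for stopping the treatment protocol will be recorded and study endpoints will be collected". For methyldopa, "No additional escalation in dose in the first 6 hours will be given", whereas nifedipine and labetalol each allow two further hourly doses. A change from methyldopa to nifedipine or labetalol is described, but only for women not at goal at 6h.

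Protocol, Proposed Analyses: "The primary analysis will be done according to intention to treat". Also: "If indicated, a secondary, per protocol analyses will be performed".

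Protocol, Objectives: the primary aim is to compare the efficacy of the three oral drugs. The need for additional antihypertensive treatment belongs to a secondary aim.

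**The concern.** Put together, these statements score a woman by where her blood pressure goes and not by what took it there. Suppose her regimen is abandoned at 3h as ineffective, she is given something else, and she enters the range at 5h with no listed adverse event. She meets the success definition and is counted in her allocated arm. The more often a drug fails early, the more of its recorded successes can belong to another drug, so the difference between arms shrinks.

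The exposure is plausibly greatest for methyldopa. It has no escalation for 6h, and the Pilot Study section records doubts about its speed of onset and potency. The interim stopping guideline (Data Monitoring Committee) uses the same primary outcome, so it would inherit the dilution.

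**Working it through.** **1. Reproduce the design.** Inputs from Sample Size Calculation: 75% nifedipine v 62.5% comparator, two-sided 0.05 with Bonferroni for two comparisons (0.025 each), power 80%. With pooled variance under the null, p̄ = 0.6875 and

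n = [2.2414 × √(2 × 0.6875 × 0.3125) + 0.8416 × √(0.75 × 0.25 + 0.625 × 0.375)]² / 0.125² = 260.1, so 261 per arm.

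This matches the protocol. Power at 261 is 80.2%.

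**2. Add rescue.** Let f be the share of all methyldopa women rescued before 6h who would otherwise have failed, and c the share of these who then reach target. Neither is in the protocol; both are assumed.

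- Methyldopa-only rescue: pM = 0.625 + c·f and pN = 0.75.
- Same share of non-responders rescued in both arms: s = f / 0.375, pM = 0.625 + 0.375·s·c and pN = 0.75 + 0.25·s·c. The difference is 12.5 × (1 − s·c) points.

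Power at n = 261, two-sided 0.025 = Φ{[(pN − pM)√n − 2.2414√(2p̄(1 − p̄))] / √(pN(1 − pN) + pM(1 − pM))}.

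Example, f = 10%, c = 70%, methyldopa only: pM = 0.695, difference 0.055, p̄ = 0.7225. The argument is (0.8886 − 1.4193) / 0.6320 = −0.840, so power is 20%.

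| f (share of the 37.5% non-responders) | Methyldopa only, c = 70%: rate, difference, power | Methyldopa only, c = 40%: rate, difference, power | Both arms, c = 70%: rates N v M, difference, power |
|---|---|---|---|
| 0 | 62.5%, 12.5, 80% | 62.5%, 12.5, 80% | 75.0 v 62.5%, 12.5, 80% |
| 5% (13%) | 66.0%, 9.0, 51% | 64.5%, 10.5, 65% | 77.3 v 66.0%, 11.3, 74% |
| 10% (27%) | 69.5%, 5.5, 20% | 66.5%, 8.5, 46% | 79.7 v 69.5%, 10.2, 67% |
| 15% (40%) | 73.0%, 2.0, 4% | 68.5%, 6.5, 28% | 82.0 v 73.0%, 9.0, 59% |

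Differences are in percentage points. Even when rescue is equally frequent among non-responders, the arm with more non-responders gains more.

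**3. Would the per-protocol analysis correct this?** The protocol does not define it. If it drops women whose regimen was stopped, then at f = 10% the methyldopa rate becomes 62.5 / 90 = 69.4%, almost the same as the 69.5% above. Removing failures from the denominator does not restore them as failures.

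**The case against.** **The protocol never says such a woman is a success.** True. It is silent on her, and the conclusion comes from applying its definition to a case it does not mention. An analysis plan that is not shown could add a rule. But the protocol itself fixes the outcome, the list of cancelling events and the analysis set, and a plan that follows them inherits the gap.

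**A pragmatic trial may want the outcome regardless of rescue.** That is a recognised choice, and the Design section does call the trial pragmatic. The aim and hypothesis, however, concern the efficacy of each drug, and additional treatment is placed under a secondary aim. That aim would make unequal rescue visible, but would not change the primary score.

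**A reader might infer that methyldopa failures are switched to nifedipine or labetalol before 6h.** The text does not support this. That switch is stated only for failure at 6h, and the drug given after an earlier stop is not named. The stopping criterion is narrow, requiring clinically unsafe pressures. The other two arms are exposed as well, since their scheduled extra doses can be used up about 2h after the first. That methyldopa is worst affected is a reasonable inference, not a stated fact.

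**A reader might also infer that the result is likely to reverse.** With c = 70% and rescue on methyldopa only, reversal needs more than 12.5 / 0.70 = 17.9% of that arm rescued, or 48% of its non-responders, and none on nifedipine. Nothing in the protocol supports such a rate. With equal rescue shares the difference cannot change sign.

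**The first scenario is an extreme.** This stands. It assumes no nifedipine rescue and that every rescued woman would have failed, although slow onset means some could have reached target later. It also gives women with unsafe pressures and less time left a conversion rate close to the planning rates. The other two scenarios are shown for this reason.

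**Conclusion.** The gap is real and worth closing. Applied as written, the success definition, intention to treat and permitted early discontinuation leave nothing to stop a rescue success being credited to the allocated drug. The effect is dilution of the efficacy contrast in favour of the weaker drug.

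Its size cannot be derived from the protocol. For 5 to 15% of methyldopa women rescued, power ranges from 74% down to 4% depending on conversion and on whether nifedipine women are rescued too. The low end rests on rescue confined to methyldopa with 70% conversion. The protocol's sample size arithmetic is correct and not in question.

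**What to change.** Add one sentence to the primary definition wherever it appears (Study Outcomes, Sample Size Calculation, Proposed Analyses, Data Monitoring Committee). A woman who, within 6h and before first meeting the target, receives an antihypertensive outside her allocated regimen, or has that regimen stopped for ineffective response, is a non-success and stays in the intention-to-treat denominator. The Data Monitoring Committee section words the outcome as at 6h where the others say within 6h; align it so that the sentence has one meaning.

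Report the result regardless of rescue as a sensitivity analysis. Leave side-effect stops to the existing adverse-outcome list unless another antihypertensive is given; the argument here does not reach them.

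Costs:

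- **Data.** Form 2 times each dose and Form 7 records discontinuation, but the protocol does not say that either captures the name and time of a non-allocated antihypertensive. Confirm this or add the field.
- **Success rates.** They may come out slightly lower. The planned 75% and 62.5% then describe the allocated drug, and 261 per arm stands.
- **Open label.** Providers know the allocation and the protocol voices doubts about methyldopa, so a decision to stop or rescue can itself create a failure, a bias in the opposite direction. Report reasons for stopping and blood pressure at the stop by arm, beside the sensitivity analysis.

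This changes scoring only. Dosing, rescue and the decision to stop remain as they are.
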